5.1 Overall Design

This is a Phase 1b/2a, non-randomized 2 arm, open label multi-institutional trial. The dose escalation phase (Phase 1b) of the study will determine the MTD or RP2D of NT-I7 in combination with atezolizumab. The Phase 2a will be a non-randomized parallel dose expansion phase to confirm the MTD or RP2D in both arms.

A total of approximately 84 patients will be enrolled; up to approximately 24 patients will be enrolled in the Phase 1b (a 3+3 dose escalation design will be used), and approximately 60 patients will be enrolled in the Phase 2a (24 patients in Arm I, i.e., 12 patients for each indication, and 36 patients in Arm II, i.e., 12 patients for each indication).

Arm I: Anti-PD-1/PD-L1 (CPI) naïve patients with cSCC and MCC

[figure not shown]
Arm II: Anti-PD-1/PD-L1 relapsed/refractory patients with MCC, cSCC and melanoma

^aNT-I7 Dose Interruption

NT-I7 administration will be skipped when the ALC is higher than 10,000 cells/µL on Day 1 of every other cycle, starting on Cycle 3. Blood draws conducted prior to dosing on Day 1 will determine if NT-I7 should be interrupted for the current cycle.

^bStarting with DL4 (1200 µg/kg), NT-I7 dosing is changed from Q3W to Q6W. Atezolizumab dosing remains the same (Q3W).

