Treatment Cycle/Visit	Screening	Cycle 1		Cycle 2		Cycle 3		Cycle 4	Cycle 5	Subsequent Cycle (Repeat up to 2 year)	End of Tx	Safety FU	Disease Assessment	Survival FU
Scheduling Window	Within 7 days	Day 1	Day 2	Day 8± 2 days	Day 1± 2 days	Day 8± 2 days	Day 1± 2 days	Day 8± 2 days	Day 1± 2 days	Day 1± 2 days	30 days ± 5 days post Tx	60 and 90 days ± 7 days post Tx	Every 12 wks ± 1 wk	Every 12 wks ± 1 wk
Hepatitis B testing	X													
Efficacy Measurements														
Tumor measurements	Within 28 days	Tumor measurements are performed at 9 weeks ± 1 week for the first two timepoints, then every 12 weeks ± 1 week . Documentation (radiologic) must be provided for patients removed from study for progressive disease.										X	X	X
Radiologic evaluation	Within 28 days	Radiologic measurements should be performed at 9 weeks ± 1 week for the first two timepoints, then every 12 weeks ± 1 week										X	X	X
Tumor Biopsy	X ^d							X ^d						
Tumor Biopsies/Archival Tissue Collection														
T-cell count (CD4+ and CD8+)		X ^e			X ^e			X ^e		X ^e	X ^e	X ^e	X ^e	
Pharmacokinetics ^h	X	X ^{**}	X			X			X	X				X
Immunophenotyping	X		X ^k	X		X	X	X	X	X				X
Multiplex Cytokines	X			X		X		X	X	X				X
TCR sequencing	X			X		X		X	X	X				
Correlative Studies Blood Draws^e														

Statistical Analysis Plan Template

Sponsor:	NeolimmuneTech, Inc.		
Protocol:	NTT-106 (ION-02)		
Document Version No.:	1.0	Document Date:	20Nov2023

ARM I AND ARM II										Post-Treatment Follow-up							
Treatment Cycle/Visit	Screening	Cycle 1		Cycle 2		Cycle 3		Cycle 4		Cycle 5		Subsequent Cycle (Repeat up to 2 year)	End of Tx	Safety FU	Disease Assessment	Survival FU	
		Within 7 days	Day 1	Day 2	Day 8± 2 days	Day 1± 2 days	Day 8± 2 days	Day 1± 2 days	Day 8± 2 days	Day 1± 2 days	Day 1± 2 days						
Scheduling Window													30 days ± 5 days post Tx	30 days ± 5 days post Tx	60 and 90 days ± 7 days post Tx	Every 12 wks ± 1 wk	Every 12 wks ± 1 wk
ELISPOT	X				X		X		X		X						
Kyn/Trp and Arginine	X				X		X		X		X						
Immunogenicity Testing ^g (NT-17)	X				X		X		X		X		X	X	X		

A NT-17: Dose as assigned; starting with DL4 (1200 µg/kg), NT-17 dosing is changed from Q3W to Q6W (i.e., Cycle 1, Day 1, Cycle 3, Day 1, Cycle 5, Day 1, etc.). NT-17 will be skipped when the ALC is higher than 10,000 cells/µL on Day 1 of each cycle, starting on Cycle 3 (protocol Section [5.2](#)).

* NT-17 must be administered 60 (± 10) minutes before atezolizumab.

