4.2. General Statistical Methods and Data Handling

4.2.1. General Methods

All output will be incorporated into RTF or PDFs, sorted and labeled according to the International Conference on Harmonisation (ICH) recommendations, and formatted to the appropriate page size(s).

Phase 1b/dose escalation will be presented by dose levels 120 µg/kg, 360 µg/kg, 840 µg/kg, 1200 µg/kg and Total. Phase 2a/dose expansion will be summarized under the 1200 µg/kg dose. Efficacy analysis will analyze two groups of pooled data. The first group will pool 120 µg/kg, 360 µg/kg, and 840 µg/kg doses levels of Phase 1b; and the second group will pool the 1200 µg/kg dose level from both phases.

For categorical variables, summary tabulations of the number and percentage within each category (with a category for missing data) of the parameter will be presented.

Continuous variables will be summarized using mean, standard deviation, median, inter-quartile range (IQR) and range; 95% confidence intervals will be presented where appropriate.

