4.2.11. Years and Months

For any calculations, Years will be 365.25 days and Months will be 30.4375 (or 365.25/12).

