4.7. Study Treatment

Dose intensities will be summarized based on the Safety Population, with phases 1b and 2a presented separately by dose level/arm. Patients who have completed each cycle will be summarized.

The dose intensity of NT-17 and atezolizumab is defined as:

Total actual dose received /duration of treatment(months); where treatment duration is last dose date – first dose date + 1

Dose intensity will be summarized overall for each product.

Study treatment data will be included in a by-patient listing.

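### SAP 4.7 stops treatment duration at the last dose date, so dose intensity is overstated for every compliant patient, and most for those who stop earliest

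*SAP*

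**What the plan says.** SAP 4.7 gives one formula for NT-I7 and atezolizumab: "Total actual dose received /duration of treatment(months); where treatment duration is last dose date – first dose date + 1". SAP 4.2.11 sets a month at 30.4375 days. On presentation, SAP 4.7 says "Dose intensities will be summarized based on the Safety Population, with phases 1b and 2a presented separately by dose level/arm" and "Dose intensity will be summarized overall for each product". It does not say whether the first and last dose dates belong to the product being summarized or to either agent. It defines no relative dose intensity (actual over planned) and no allowance for the last dosing interval.

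The Safety Population (SAP 3.1.1) needs only one dose. SAP 4.2.1 says "Continuous variables will be summarized using mean, standard deviation, median, inter-quartile range (IQR) and range", so a mean is planned beside the median.

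The two products differ in interval, and so do the NT-I7 dose levels. Footnote A to the schedule in SAP 2.4 records that from 1200 µg/kg "NT-17 dosing is changed from Q3W to Q6W" (the SAP prints NT-I7 with a digit 1). Protocol 5.1 agrees and keeps atezolizumab at Q3W. Dose levels 1 to 3 (120, 360 and 840 µg/kg) were therefore planned Q3W; dose level 4 (DL4) and Phase 2a are Q6W.

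**The concern.** An intermittently dosed drug is delivered at a rate of one dose per interval. If n doses are divided by a duration that spans only n − 1 intervals plus one day, the rate comes out too high. The error is largest with few doses, and it depends on the interval.

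Two things are at stake. First, a patient who stops after one dose has a duration of one day and appears the most intensively treated in the column. The Safety Population includes such patients, and the planned mean gives them heavy weight. Second, the columns mix Q3W and Q6W regimens, and SAP 5 puts all phases in one table, so a reader will compare DL4 with dose level 3 (DL3). If the inflation differs between them, the comparison misleads.

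**Working it through.** **Inputs.** Formula: SAP 4.7. Month M = 30.4375 days: SAP 4.2.11. Doses 120, 360, 840 and 1200 µg/kg: protocol 5.2.2. Intervals of 21 days (Q3W) and 42 days (Q6W): protocol 5.1 and Table 3. The documents give no dose-intensity figure, so there is none to reproduce. I assume on-time dosing, dose expressed per kg, and no schedule switch at DL1 to DL3.

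**Planned rate**, D × M / τ for dose D and interval τ:
- 840 Q3W: 840 × 30.4375 / 21 = 1217.5 µg/kg/month
- 1200 Q6W: 1200 × 30.4375 / 42 = 869.6 µg/kg/month
- DL4/DL3 = 869.6 / 1217.5 = 0.714, that is, 29% lower

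**SAP formula, per-product dates.** After n on-time doses the duration is (n − 1)τ + 1 days, so intensity is nDM / ((n − 1)τ + 1). Relative to plan it is nτ / ((n − 1)τ + 1), in which D and M cancel. This exceeds 1 for every n.

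| Doses | 1200 Q6W, µg/kg/month | Times plan | 840 Q3W, µg/kg/month | Times plan |
|---|---|---|---|---|
| 1 | 36,525 | 42/1 = 42.0 | 25,567.5 | 21/1 = 21.0 |
| 2 | 1698.8 | 84/43 = 1.95 | 2324.3 | 42/22 = 1.91 |
| 3 | 1289.1 | 126/85 = 1.48 | 1783.8 | 63/43 = 1.47 |
| 4 | 1150.4 | 168/127 = 1.32 | 1598.0 | 84/64 = 1.31 |
| 9 | – | 378/337 = 1.12 | – | 189/169 = 1.12 |

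The one-dose row applies to Q6W patients who stop before C3D1 (day 43) and Q3W patients who stop before C2D1 (day 22). Atezolizumab follows the Q3W ratios.

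**DL4 against DL3, compliant patients, same number of cycles, per-product dates:**
- Through cycle 2 (1 dose against 2): 36,525 / 2324.3 = 15.7
- Through cycle 3 (2 against 3): 1698.8 / 1783.8 = 0.95
- Through cycle 4 (2 against 4): 1698.8 / 1598.0 = 1.06

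After cycles 2 and 4 the ratio should be 0.714. At 24 weeks (4 doses against 8) it is 1 / 1.201 = 0.83, so the distortion fades with time.

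**SAP formula, either-agent dates.** DL4 duration now follows atezolizumab:
- Through cycle 2: 1200 × 30.4375 / 22 = 1660.2, which is 1.91 times plan; DL4/DL3 = 1660.2 / 2324.3 = 0.714
- Through cycle 4: 2400 × 30.4375 / 64 = 1141.4, which is 1.31 times plan; DL4/DL3 = 1141.4 / 1598.0 = 0.714

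Both levels are inflated, but their ratio equals the delivered-dose ratio (1200/1680 and 2400/3360). The factors 42 and 21 then apply only to patients dosed on C1D1 alone.

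**Skipped dose.** Protocol 5.2.1 and 5.3.1 skip NT-I7 from C3D1 when ALC exceeds 10,000 cells/µL. Take Q6W doses on days 1 and 85 with C3D1 skipped. The SAP value is 2400 × 30.4375 / 85 = 859.4, which is 0.99 of the planned rate. A compliant patient with the same first and last dates scores 1289.1, and 859.4 / 1289.1 = 0.667.

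**Corrected duration.** Counting one interval after the last scheduled dosing day gives nτ days for a compliant patient, hence a ratio of 1.00 for any n on either schedule. For the skipped-dose patient, 85 − 1 + 42 = 126 days, 2400 × 30.4375 / 126 = 579.8, and 579.8 / 869.6 = 0.67.

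**The case against.** The strongest reply is that much depends on an unsettled reading. SAP 4.7 speaks of a single treatment duration, and SAP 4.2.10 anchors C1/D1 to the first dose of any study treatment, so either-agent dates are arguable. A reader might infer that the table misstates the Q3W against Q6W difference whichever dates are used. The documents do not support that: with either-agent dates, matched-cycle ratios are the delivered-dose ratios. A reader might also take 42 times as the error for Q6W patients generally; it is the one-dose extreme and falls below 2 at the second dose.

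It is also tempting to say that the formula hides ALC skips. The score of 0.99 comes from dividing by a planned rate that the SAP does not report. Against a compliant patient with the same dates, the missed third is fully visible.

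There are safeguards too. The median and IQR accompany the mean, and SAP 4.7 also plans cycle-completion counts and a by-patient treatment listing. No regimen comparison or p-value is planned. A reader might suspect the efficacy results because SAP 4.2.1 says "Efficacy analysis will analyze two groups of pooled data", but dose intensity is not an input to those summaries, which use a different population.

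All of this limits the point. It does not remove it: under either reading a compliant patient's intensity is overstated, and listings do not correct a summary statistic.

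**Conclusion.** The formula is wrong as written for intermittent dosing. Under the per-product reading, which the summary for each product makes the natural one, the overstatement for compliant patients runs from 42 or 21 times after one dose to about 1.3 times after four and 1.12 after nine. DL4 can then appear about equal to or above DL3 through the first four cycles, although its planned rate is 29% lower. Under the either-agent reading the overstatement remains (1.91 times after two cycles, 1.31 after four), without distortion between levels at matched cycles.

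The consequence is confined to a descriptive exposure table, and the other planned exposure outputs partly reveal it. DLT and MTD decisions, ORR, PFS and OS are unaffected. The figures rest on on-time dosing, dose per kg, and DL1 to DL3 patients staying on Q3W; the documents do not say whether any switched. The number of one-dose patients is not known from the documents, so the size of the effect on the column means cannot be stated.

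**What to change.** In SAP 4.7, state that dates are per product and define duration as Day 1 of the last cycle in which that product was scheduled while the patient was on treatment (given or skipped), minus first dose date, plus the dosing interval. The interval is 21 days for atezolizumab and NT-I7 Q3W, and 42 days for NT-I7 Q6W.

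Report number of doses, cumulative dose, and relative dose intensity against the assigned regimen. Planned rates are 173.9 (120 × 30.4375 / 21), 521.8 (360 × 30.4375 / 21) and 1217.5 µg/kg/month for the Q3W levels, 869.6 for 1200 µg/kg Q6W, and 1739.3 mg/month for atezolizumab (1200 × 30.4375 / 21).

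The cost is one derivation and one table shell, using dose dates and amounts already collected, with no protocol amendment. Any dose-intensity output already produced under SAP version 1.0 must be rerun, and each DL1 to DL3 patient's schedule must be confirmed from the dosing records.

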4.8. Efficacy Evaluation

All Efficacy analysis will be assessed using the Efficacy Population, unless specified otherwise.

Time to event data will be summarized using Kaplan-Meier Methodology using 25th, 50th (median), and 75th percentiles with associated 2-sided 95% confidence intervals, as well as percent of censored observations. The survival curves will be generated using the Kaplan-Meier method. The rate at 3, 6, 9, 12, 18 and 24 months will be calculated for PFS and OS.

4.8.1. Objective Response Rate and Disease Control Rate

ORR is defined as the percentage of patients who have at least one confirmed partial response (PR) or complete response (CR) according to RECIST v1.1 as determined by the investigator.

DCR is defined as percentage of patients with a response of CR, PR or Stable Disease (SD) according to RECIST v1.1.

The best overall response (BOR) is the best response recorded from the start of the treatment until disease progression/recurrence. Patients without baseline or post-baseline assessments will be considered Not Evaluable (NE).

The number and percentage of patients in each BOR category (CR, PR, SD, PD, NE), and ORR and DCR will be presented.

Listings of tumor assessments and responses assessment will be provided.

Sponsor:	NeolimmuneTech, Inc.		
Protocol:	NIT-106 (ION-02)		
Document Version No.:	1.0	Document Date:	20Nov2023

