Based on the available data provided in Section 2.2, the average historical ORR for the patients in this study would be 45.25% in Arm I and less than 5% in Arm II. With a total of 24 patients treated at the RP2D in Phase 2a of the study in Arm I, the 95% confidence interval for an observed ORR of 17/24 or higher would exclude 45.25%. With a total of 36 patients treated at the RP2D in Phase 2a of the study in Arm II, the 95% confidence interval for an observed ORR of 6/36 or higher would exclude 5%.

Approximately 84 patients will be enrolled in this study; up to approximately 24 patients in the Phase 1b and approximately 60 evaluable patients in the Phase 2a of the study. The expected accrual is 4 patients per month total at approximately 8 ION sites.

Safety Population: All patients who receive at least 1 dose of the investigational regimen will be considered evaluable for safety and included in the overall safety analysis. For the Phase 1b, in the absence of a DLT, patients must complete the full 3-week DLT window period to be considered evaluable for DLTs. Patients who discontinue from the study before the completion of the full 3-week (21 days) DLT window for reasons other than the occurrence of a DLT (e.g., withdrawal of consent, rapid tumor progression, death due to rapid tumor progression, AE that does not meet DLT criteria) will not be considered evaluable for DLTs and will be replaced.

Efficacy Population: The efficacy analysis for the Phase 1b (dose escalation) portion will be conducted on all DLT-evaluable patients, as defined in Section 6.2.2. The efficacy analysis for the Phase 2a (expansion phase) portion will be conducted on all patients who received at least one cycle of study treatment and have at least one evaluable post baseline tumor assessments.

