15.6 Reporting and Exclusions

15.6.1 Evaluation of Toxicity

All patients will be evaluable for toxicity from the time of their first treatment with atezolizumab and/or NT-I7 until 30 days after the last dose of study treatment.

15.6.2 *Evaluation of Response*

All patients enrolled in the study who received at least 1 cycle of study treatment will be assessed for response to treatment, even if there are major protocol treatment deviations or if they are ineligible. Each patient will be assigned one of the following categories: (1) CR, (2) PR, (3) SD, (4) PD, (5) early death from malignant disease, (6) early death from toxicity, (7) early death because of other cause, or (9) unknown (not assessable, insufficient data). [Note: By arbitrary convention, category 9 usually designates the “unknown” status of any type of data in a clinical database.]

All of the patients who met the eligibility criteria and received at least 1 dose of study treatment will be included in the main analysis of the response rate. Patients in response categories 4-9 should be considered to have a treatment failure (disease progression). Thus, an incorrect treatment schedule or drug administration does not result in exclusion from the analysis of the response rate. Precise definitions for categories 4-9 will be protocol specific.

All conclusions should be based on patients who received at least 1 cycle of study treatment. Sub-analyses may then be performed on the basis of a subset of patients, excluding those for whom major protocol deviations have been identified (early death due to other reasons, early discontinuation of treatment, major protocol violations, *etc.*). However, these sub-analyses may not serve as the basis for drawing conclusions concerning treatment efficacy, and the reasons for excluding patients from the analysis should be clearly reported. The 95% confidence intervals should also be provided.

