4. STATISTICAL METHODS

4.1. Sample Size Justification

During the dose escalation phase (Phase 1b), a 3+3 design will be used for identifying the MTD and/or the RP2D. The following design will be used:

Number of Patients with Dose-Limiting Toxicity (DLT) at a Given Dose Level	Escalation Decision Rule
0 out of 3	Enroll 3 patients at the next dose level.
1 out of 3	Enroll at least 3 more patients at this dose level. 
- If 0 of these 3 additional patients experience a DLT (totaling 1/6), enroll at the next dose level.- If ≥ 1 of these 3 additional patients experiences DLT (totaling $\geq 2/6$ at the dose level), the dose escalation is stopped, and the next lower dose level will be declared the MTD. In the case this happens at the 120 $\mu\text{g}/\text{kg}$ dose level, a lower dose of 60 $\mu\text{g}/\text{kg}$ will be tested, and the same 3+3 design followed.
≥ 2 out of 3	Dose escalation will be stopped. The next lower dose level will be declared the MTD. Three (3) additional patients will be entered at the next lower dose level if only 3 patients were treated previously at that dose. In the case this happens at the 120 $\mu\text{g}/\text{kg}$ dose level, a lower dose of 60 $\mu\text{g}/\text{kg}$ will be tested, and the same 3+3 design followed.

Based on the available data (Section 2.2 of the protocol), the average historical ORR for the patients in this study would be 45.25% in Arm I and less than 5% in Arm II. With a total of 24 patients treated at the RP2D in Phase 2a of the study in Arm I, the 95% confidence interval for an observed ORR of 17/24 or higher would exclude 45.25%. With a total of 36 patients treated at the RP2D in Phase 2a of the study in Arm II, the 95% confidence interval for an observed ORR of 6/36 or higher would exclude 5%.

Sponsor:	NeolimmuneTech, Inc.		
Protocol:	NIT-106 (ION-02)		
Document Version No.:	1.0	Document Date:	20Nov2023

Approximately 84 patients will be enrolled in this study; up to approximately 24 patients in the Phase 1b and approximately 60 patients in the Phase 2a of the study. The expected accrual is 4 patients per month total at approximately 8 ION sites.

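### SAP 4.8.1 reports ORR and DCR without a confidence interval, although the Phase 2a sample size is justified by one, and no interval method is named

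*SAP*

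**What the plan says.** Protocol Table 2 makes investigator-assessed ORR the Phase 2a primary endpoint. Its sample size is justified in SAP 4.1, and in the same terms in Protocol 15.3. The starting point is that "the average historical ORR for the patients in this study would be 45.25% in Arm I and less than 5% in Arm II". For Arm I, "the 95% confidence interval for an observed ORR of 17/24 or higher would exclude 45.25" (per cent). For Arm II, "the 95% confidence interval for an observed ORR of 6/36 or higher would exclude 5" (per cent). Neither document gives a target ORR, a power figure or an interval method.

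The text on response evaluation in Protocol 15.6.2 closes with "The 95% confidence intervals should also be provided". Protocol 15.5.1 wants the Phase 2a analyses, ORR among them, done for each arm on its own.

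On the SAP side:

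- 4.8.1 sets the output for response: "The number and percentage of patients in each BOR category (CR, PR, SD, PD, NE), and ORR and DCR will be presented".
- 4.2.1 says that for categorical variables "summary tabulations of the number and percentage within each category (with a category for missing data) of the parameter will be presented". The clause "95% confidence intervals will be presented where appropriate" comes in the next sentence, which is about continuous variables.
- 4.8 specifies intervals for time-to-event endpoints: "25th, 50th (median), and 75th percentiles with associated 2-sided 95% confidence intervals".
- 4.2.1 also pools efficacy into two dose groups, the second combining 1200 µg/kg from both phases. 4.2.6 plans no subpopulation analyses.
- Section 5 lists the departures from the protocol that follow from early closure. Dropping an interval for ORR is not among them.

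**The concern.** The time-to-event endpoints have a specified interval and the Phase 2a primary endpoint has none. Followed literally, the SAP produces a response percentage and leaves out the comparison on which the design was based. With few responses, a bare percentage also hides how imprecise the estimate is.

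If someone adds an interval later, they must choose the method after seeing the data. With samples this small, the choice can decide whether a benchmark falls inside or outside the interval.

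**Working it through.** **Inputs** (Protocol 15.3, SAP 4.1): Arm I n = 24, reference 45.25%, stated count 17. Arm II n = 36, reference 5%, stated count 6. All intervals are two-sided 95%, z = 1.96, p = x/n.

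**Lower-limit formulas**

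- Clopper-Pearson: the 2.5% quantile of Beta(x, n − x + 1).
- Wald: p − z√[p(1 − p)/n].
- Wilson: {p + z²/2n − z√[p(1 − p)/n + z²/4n²]} / (1 + z²/n).

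**Step 1: reproduce the stated counts.** Clopper-Pearson gives lower limits of 44.68% at 16/24 and 48.91% at 17/24, so 17 is the smallest count that excludes 45.25%. It gives 4.67% at 5/36 and 6.37% at 6/36, so 6 is the smallest that excludes 5%. The binomial upper tails agree. At a true rate of 45.25%, P(X ≥ 16) = 0.0285 and P(X ≥ 17) = 0.0102. At 5%, P(X ≥ 5) = 0.0324 and P(X ≥ 6) = 0.0083. In each arm the stated count is the first to fall below 0.025.

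**Step 2: try other methods.** Two worked cases:

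- Wald at 6/36: 0.1667 − 1.96 × √(0.1667 × 0.8333/36) = 0.1667 − 1.96 × 0.0621 = 0.0449. This does not exclude 5%.
- Wilson at 16/24: (0.6667 + 0.0800 − 0.2049)/1.1601 = 0.4671. This excludes 45.25%.

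| Lower 95% limit | Clopper-Pearson | Wilson | Wald |
|---|---|---|---|
| 16/24 (vs 45.25%) | 44.68% | 46.71% | 47.81% |
| 17/24 (vs 45.25%) | 48.91% | 50.83% | 52.65% |
| 5/36 (vs 5%) | 4.67% | 6.08% | 2.59% |
| 6/36 (vs 5%) | 6.37% | 7.87% | 4.49% |
| 7/36 (vs 5%) | 8.19% | 9.75% | 6.52% |
| Smallest qualifying counts (Arm I, Arm II) | 17, 6 | 16, 5 | 16, 7 |

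Continuity-corrected Wald and Wilson, Agresti-Coull, Jeffreys, mid-P and one-sided 95% Clopper-Pearson were also tried. None gives both 17 and 6 as the smallest counts.

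**Step 3: other denominators.** SAP section 5 reports premature closure, so 24 and 36 may not be reached. The sizes below are assumptions, for illustration only.

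| Assumed n | Clopper-Pearson | Wilson | Wald |
|---|---|---|---|
| Arm I, 12 | 10 | 9 | 9 |
| Arm I, 20 | 14 | 14 | 14 |
| Arm I, 22 | 16 | 15 | 15 |
| Arm II, 20 | 4 | 3 | 5 |
| Arm II, 30 | 5 | 4 | 6 |
| Arm II, 34 | 6 | 5 | 7 |

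The printed counts do not carry over to other sizes. At most of these sizes the methods differ by one or two responses.

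**The case against.** The case against has four parts.

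1. **There is no decision rule.** A reader might infer that 17/24 and 6/36 are success thresholds. The documents do not support that. The counts appear only under sample size, nothing calls them a go/no-go criterion, SAP 4.2.5 says that no p-values will be reported, and Protocol 15.5.1 describes the analyses as descriptive. This stands.
2. **The comparison is still possible.** A reader might infer that the benchmarks cannot be used without a tabulated interval. That goes too far. Given a count and a denominator, anyone can check the count or compute an interval, and SAP 4.8.1 also promises response listings. This stands, but whoever computes the interval then picks the method.
3. **The stated counts are mostly robust.** At 17/24 every method tried excludes 45.25%. At 6/36 Clopper-Pearson, Wilson and Jeffreys exclude 5%, and only the Wald forms, plain or continuity-corrected, do not. The documents also never say that 17 and 6 are the smallest qualifying counts, so it would be wrong to say their statements are true only with exact limits. This stands: the other reversals occur at 16/24 and 5/36, just below the stated counts.
4. **The interval may already be covered.** Protocol 15.6.2 asks for intervals and the SAP does not withdraw the request; the clause in SAP 4.2.1 could be read broadly. This is weak. The 15.6.2 sentence directly follows text on sub-analyses, so its reach is arguable, and the 4.2.1 clause sits with continuous variables. Neither names a method.

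**Conclusion.** The gap is real and should be closed. The SAP specifies a count and percentage for the Phase 2a primary endpoint, omits the interval that justifies the sample size, and does not declare this as a departure from the protocol. The unnamed method moves the smallest qualifying count between 16 and 17 in Arm I and between 5 and 7 in Arm II. The stated figures themselves are correct under two-sided Clopper-Pearson limits. That this was the method used is an inference: it is the only one tried for which both counts are minimal.

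Pooling makes the gap larger. The 1200 µg/kg group mixes both Phase 2a arms with Phase 1b patients, while the benchmarks of 45.25% and 5% belong to Arm I and Arm II separately. An interval for the pooled group alone would not serve the comparison.

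The calculations rest on the printed sizes of 24 and 36. With early closure the final denominators are not known from these documents, which is a further reason to fix a method and not rely on the printed counts.

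**What to change.** Add to SAP 4.8.1:

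> ORR and DCR will be presented with two-sided exact (Clopper-Pearson) 95% confidence intervals, separately for each Phase 2a arm (Protocol 15.5.1) as well as for the pooled dose groups. The Arm I and Arm II ORR intervals will be set against 45.25% and 5% respectively.

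Name Clopper-Pearson in SAP 4.1 as the basis of the two counts, and in Protocol 15.3 if the protocol is amended again. No stated number changes.

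The cost is a few extra table columns, including the by-arm display, and intervals slightly wider than Wilson or mid-P would give.
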